Fig 2.6: The effect of betamethasone valerate (0.1%) cream (BMVc) and Tacrolimus (0.1%) ointment (TACo) on the water holding capacity of the SC. (a) SC hydration measured using the capacitance method. A one-way ANCOVA revealed a significant difference between the two treatments ($n = 25$, $p = 0.020$). The dashed line indicates mean capacitance before treatment. (b) The level of NMF components 2-pyrrolidone-5-carboxylic acid (PCA) and (c) urocanic acid (UCA) detectable in the SC, as measured *ex vivo* by HPLC ($n = 25$). BMVc significantly lowered PCA (**** $p < 0.0001$) and UCA (* $p < 0.05$) levels compared to untreated skin. For clinical relevance both PCA and UCA were quantified in *FLG* mutation carriers ($n = 6$) with active AD at non-lesional sites (NL-AD). ⁺All groups were significantly different from NL-AD (* $p < 0.05$).

[figure not shown]

Fig 2.7: (Left) Representative raw B scan of epidermis (highlighted) determined by structural OCT. **(Right)** Change in epidermal thickness following a 4-week, twice-daily treatment regimen using betamethasone valerate (0.1%) cream (BMV) and Tacrolimus (0.1%) ointment (TAC).

The suppression of NMF is important for 2 reasons: (1) NMF plays an important role in skin barrier homeostasis (pH regulation) and moisturization and (2) NMF is a downstream product of Filaggrin catabolism and so its reduction suggests a decrease in filaggrin levels/ *FLG* gene (encoding filaggrin) expression. Reduced filaggrin levels/ *FLG* gene expression is a key cause of skin barrier dysfunction, and patients exhibiting a deficit of functional filaggrin are predisposed to more severe, persistent, AD, depending on the extent of the deficit. What is not clear from the literature is whether filaggrin function itself is important, or its role in providing the material for NMF or a combination of both (the latter being most likely) due to the pivotal functions of both filaggrin and NMF.

Together the data clearly evidences the negative local adverse effects of topical corticosteroids, which can worsen AD after the ant-inflammatory effects have waned following TCS discontinuation, and helps establish a set of benchmarks upon which to compare alternative topical ant-inflammatory treatments.

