4.5 Secondary endpoint/outcome

- The difference in the change in epidermal thickness measured by structural OCT during and after 28 days treatment. OCT images of epidermal thickness taken on day 1, day 15, day 29 and day 57.
- The difference in the change in skin redness/erythema (relating to tolerability) during and after 28 days treatment determined by:
 - Visual redness/erythema score determined on day 1, day 15, day 29 and day 57
 - Objective redness assessed with the Mexameter measured on day 1, day 15, day 29 and day 57
- The difference in the change in Trans-Epidermal Water Loss (TEWL, relates to skin barrier function) during and after treatment.^{17,18} TEWL measurements on day 1, day 15, day 29 and day 57.
- The difference in skin barrier integrity (TEWL_{t=20}) after 28 days treatment. TEWL measurements after tape-stripping (TEWL_{t=20}) on day 29
- The difference in the change in visual skin dryness during and after treatment. Visual skin dryness scored on day 1, day 15, day 29 and day 57
- The difference in Natural Moisturising Factor (NMF, filaggrin breakdown products) levels at the end of treatment¹⁹ NMF will be quantified from superficial stratum corneum samples collected on day 29 using HPLC.

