10.4.3 Secondary outcome analysis

A this is an exploratory study investigating a number of possible biomarkers no formal adjustments for multiplicity will be made, however results will be presented alongside confidence intervals and will be interpreted cautiously. A future study is planned to confirm the selection of biomarkers from this study.

The analysis of the secondary endpoints:

- Change in structural OCT measurements of epidermal thickness
- Change in redness/erythema
- Change in Trans-Epidermal Water Loss (TEWL)
- Change in visual skin dryness
- Natural Moisturising Factor

will use paired analyses to compare the change over time between crisaborole (2%) ointment and betamethasone valerate (0.1%) cream.

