Visual scoring of the dryness of the subject's skin by an expert will take place at baseline (day 1), after 2 weeks treatment (day 15), after 4 weeks treatment (day 29) and 4 weeks after treatment cessation (day 57). Scores will be on a scale from 0 to 4 and will be graded by two observers independently. The upper and lower volar forearms on each side will be combined to give one overall result for the right and one overall result for the left.

NMF levels

Samples for analysis of stratum corneum NMF levels will be collected by tape stripping after 4 weeks of treatment (single time point, day 29). One sample will be collected from each sampling site (tape-strips/discs 1-3 on lower right and left volar forearm). The samples will be analysed separately.

Product Consumption

Product consumption will be based on the difference in weight of the ointment and cream between the start (day 1) and end (day 29) of treatment phase.

Adverse Events

Participants will record AEs throughout the study in their diaries with the information transferred to the CRF at day 29 and day 57.

FLG loss-of-function mutations

Saliva samples will be collected at baseline (day 1) to obtain genomic DNA for determination of participant FLG gene status. Samples will undergo DNA extraction and genotyping at the

University of Sheffield for the 5 common European loss-of-function FLG mutations that have been reported to confer increased AD risk.

7. Statistical Analyses

The primary and secondary analyses will identify where there is evidence of a difference between the two treatments in the change from baseline and which biomarkers are able to identify this difference in the clinical trial setting. Exploratory analyses will investigate whether a subset of the OCT endpoints can be used to non-invasively identify skin changes.

Outcome and demographic data will be summarised at each time point using appropriate descriptive statistics such as N, mean, standard deviation, minimum, lower quartile, median, upper quartile and maximum.

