7.2 Secondary Analysis

The analysis of three of the secondary endpoints will use a repeated measures mixed model with change from day 1 (to day 15, day 29, day 57) as the outcome, treatment, timepoint as factors together with a treatment by timepoint interaction, subject as a random effect and baseline as a covariate.

The model will be used to estimate the difference between treatment arms for the change from baseline to day 29.

If there is a significant difference observed in the change from baseline to day 29, then the change from day 1 to day 15, and the change from day 29 to day 57 will also be assessed. If there is no statistically significant difference in the change from baseline to day 29 then we will not test further timepoints.

Summary statistics will be presented for all timepoints.

This applies to:

- Change in epidermal thickness (change from day 1 to day 15, and from day 29 to day 57 as secondary endpoints)
- Change in redness/erythema
- Change in Trans-Epidermal Water Loss (TEWL)
- Change in visual skin dryness

The Change in TEWL_{ts20} after 28 days treatment will use an ANCOVA model with change from day 1 to day 29 as outcome, treatment as a factor, subject as a random effect and baseline as a covariate. The analysis of Natural Moisturising Factor after 28 days treatment (day 29) will

use a paired analysis (such as a t-test, depending on the distribution of the data) unless it is necessary to adjust for any covariates, in which case an ANCOVA will be used. If any of the above models do not fit satisfactorily or appear to be over fitted the analysis may be changed to look at change from baseline to day 29 and change from day 29 to 57 separately.

Since these analyses are exploratory, no adjustment for multiplicity will be made.

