14.2.1 Epidermal thickness. (Full Analysis Set)
14.2.1.1 Change in epidermal thickness during and after 4 weeks of treatment (day 15 – day 1, day 29 – day 1, day 57 – day 1) (Full Analysis Set)
14.2.1.2 Analysis of epidermal thickness change (day 15 – day 1, day 29 – day 1, day 57 – day 1) (Full Analysis Set)
Note for this table and similar tables for the secondary endpoints – only those comparisons carried out will be included – see section 7.2

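### Unless day 29 is significant, SAP 7.2 leaves the day-15 and post-treatment secondary endpoints with descriptive summaries only, and no treatment difference or confidence interval

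*SAP*

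**What the plan says.** SAP 7.2 fits one repeated-measures mixed model per outcome, with treatment, timepoint and their interaction, and takes the day-29 treatment difference from it. If that difference is significant, "then the change from day 1 to day 15, and the change from day 29 to day 57 will also be assessed". If not: "If there is no statistically significant difference in the change from baseline to day 29 then we will not test further timepoints". The rule covers epidermal thickness, redness/erythema, TEWL and visual dryness.

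The list of tables in SAP section 9 carries the rule into the output. A note under table 14.2.1.2, which extends to the similar secondary tables, says that "only those comparisons carried out will be included".

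Descriptive output does not depend on day 29. SAP 7.2 continues: "Summary statistics will be presented for all timepoints". The opening of SAP section 7 says the same: "Outcome and demographic data will be summarised at each time point using appropriate descriptive statistics". Section 9 lists change tables for days 15, 29 and 57, and by-visit figures.

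SAP 6.2 lists the day-15 and post-treatment changes as secondary endpoints. Protocol 4.5 does too, for example: "The difference in the change in skin redness/erythema (relating to tolerability) during and after 28 days treatment". The time course of epidermal thickness is itself a secondary objective (Protocol 4.2). For the secondary endpoints Protocol 10.4.3 "will use paired analyses to compare the change over time" between the two treatments. It promises confidence intervals and cautious interpretation, and makes no timepoint depend on another. SAP 7.9 records only the interim analysis as a change from the protocol.

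**The concern.** The protocol asks how the two treatments differ during and after treatment, and Protocol section 5 gives the four-week washout the purpose of showing how fast the skin recovers. Under SAP 7.2, whether those differences are estimated at all depends on a p-value at another visit. An early difference that fades, or one that appears only after treatment stops, could leave day 29 non-significant. The analysis tables would then hold no estimate or interval for it.

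Descriptive tables do not fully replace these. Arm means at day 15 give the point difference. The interval for a paired difference also needs the correlation between arms, and SAP 2.3 says nothing is available in the literature on the standard deviation of that difference. Protocol 14.2 keeps patient-level data out of the final report, so its readers could not rebuild the interval.

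**Working it through.** **Inputs from the documents** (Protocol 10.1, SAP 2.3, SAP 7.5): betamethasone change −4.44 µm; 80% reduction, so a difference of 0.80 × 4.44 = 3.55 µm; SD of change 5 µm; two-sided 5%; 80% power; 33 completers, 37 recruited.

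**Assumptions, not in the documents:** between-arm correlation ρ of 0 or 0.5 (the plan says only that it exceeds zero); correlation 0.3 to 0.7 between the day-15 and day-29 paired differences; the 3.55 µm and 5 µm figures also apply at day 15; paired t tests stand in for the mixed model.

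**1. The plan's own figure.** Parallel groups, normal approximation: n = 2 × (1.960 + 0.842)² × 5² / 3.55² = 31.1, so 32. With the t distribution, power is 79.8% at 32 and 81.1% at 33 per group, so 33 is reproduced. Dropout: 33 / 0.90 = 36.7, so 37.

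**2. Chance that day 29 is significant, 33 pairs.** The SD of the paired difference is 5 × √(2(1 − ρ)): 7.07 µm at ρ = 0 and 5 µm at ρ = 0.5. The noncentrality is 3.55 / (7.07/√33) = 2.88, or 3.55 / (5/√33) = 4.08. Power is 80% and 98%.

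**3. Chance of showing a true 3.55 µm difference at day 15** (100,000 simulated trials per scenario; ranges cover between-visit correlation 0.3 to 0.7):

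| ρ | True day-29 difference | Day 29 significant | Day 15 shown, no condition | Day 15 shown, SAP 7.2 |
|---|---|---|---|---|
| 0 | 3.55 µm | 80% | 80% | 66–71% |
| 0 | 1.775 µm | 29% | 80% | 25–28% |
| 0 | 0 | 5% | 80% | 3–4% |
| 0.5 | 3.55 µm | 98% | 98% | about 96% |
| 0.5 | 1.775 µm | 51% | 98% | 50–51% |
| 0.5 | 0 | 5% | 98% | 4–5% |

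**4. On a standardised scale.** The planned thickness effect is 3.55/7.07 = 0.50 SD at ρ = 0 and 3.55/5 = 0.71 SD at ρ = 0.5. An assumed day-15 effect of 0.6 SD lies between these. With 33 pairs the noncentrality is 0.6 × √33 = 3.45 and unconditional power is 92%. Under SAP 7.2 it is about 4–5% with no day-29 effect, about 20% if 0.2 SD remains and 37–39% if 0.3 SD remains.

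**5. What the condition buys.** Three unconditional tests per endpoint, treated as independent, have a false-positive chance of 1 − 0.95³ = 14.3% when nothing differs. The condition holds this at 5%. Once day 29 is significant, the two further contrasts are each tested at 5%: 1 − 0.95² = 9.75% if both are null.

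**6. Precision being withheld.** The expected 95% CI half-width for a paired thickness difference is 2.037 × SD/√33: about 2.5 µm at ρ = 0 and 1.8 µm at ρ = 0.5, against a planned effect of 3.55 µm.

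**Not calculated.** The documents give no effect sizes for TEWL, redness or dryness, so their loss cannot be quantified. No post-treatment scenario was simulated.

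**The case against.** The best defence is that day 29 is a sensible lead timepoint and that testing it first is legitimate. Protocol 2.2 describes atrophic change as progressive, and Protocol 3.1 places the betamethasone effects within four weeks. Ordered testing does limit false positives within an endpoint (step 5), so a reader who infers that the condition protects no error rate goes too far. This part of the defence stands. The control is partial, however: it lapses once day 29 is significant and does not run across endpoints. SAP 7.2 and 7.5 also describe these analyses as exploratory and unadjusted. Limiting p-values does not require omitting estimates.

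A reader might also infer that day-15 and post-treatment effects go unreported. They do not: summaries, change tables and by-visit figures are planned whatever day 29 shows, and a separation in the arm means would be visible. Nor would tolerability rest on one visit, because SAP 7.4 summarises adverse events linked to a test site without any condition.

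Finally, a reader might take the protocol's background as evidence that effects will be missed. Protocol 2.3 says of the local adverse effects of corticosteroids, "which can worsen AD after the ant-inflammatory effects have waned following TCS discontinuation". It attributes this to damage done during treatment, which would tend to make day 29 significant. Protocol 2.8.2 names application site reactions as the most common drug-related events with crisaborole, but gives no time course. These passages show that day 29 need not be the peak, not that it will fail.

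**Conclusion.** The point holds as one about reporting. If day 29 is not significant, named secondary endpoints at day 15 and after treatment get descriptive summaries only. Protocol 10.4.3 does not forbid a testing order, but it sets none and promises intervals, and the departure is undeclared in SAP 7.9.

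For epidermal thickness the loss is modest if the planned effect is present at day 29, since that comparison then succeeds in 80–98% of trials. It is large if an early effect has halved or gone by day 29. The fading scenarios are assumptions, and nothing in the documents says they are likely. Equally, nothing shows a large day-29 effect on TEWL, redness or dryness. The documents do not support the stronger step of requiring the testing order to be dropped for p-values, which is a trade-off the trial team may reasonably settle either way.

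**What to change.** In SAP 7.2, state that for each listed outcome the model-estimated treatment difference with 95% CI will be reported at every planned timepoint, whatever the day-29 p-value. Amend the note under table 14.2.1.2 to match. Keep day 29 as the lead timepoint. If a testing order is retained, confine it to p-values and list it in SAP 7.9.

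In the same edit, settle the post-treatment contrast. SAP 7.2 uses day 29 to day 57. SAP 6.2 uses that for epidermal thickness but change from baseline at day 57 for redness, TEWL and dryness. The analysis tables in section 9 use day 57 minus day 1 throughout. The first measures recovery after stopping and the second the difference remaining from baseline, so the SAP should say which is reported for each outcome, or report both.

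The cost is SAP wording. The treatment-by-timepoint model already yields these contrasts, and the sample size of 33 (37 recruited) is unaffected. The downside is more unadjusted intervals. If each were read as a test, the false-positive chance per endpoint could reach about 14.3% (step 5), which the cautious interpretation promised in Protocol 10.4.3 already covers.

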7.3 Exploratory Analysis

Discriminant analysis will be used to determine which of the new biomarkers provide the most informative and sensitive data pertaining to the atrophic changes induced by TCS treatment. This will be accomplished by assessing the ability of each biomarker to differentiate the skin of participants before and after treatment with the potent TCS, which is known to induce sub-clinical atrophic skin changes within the treatment window.

The endpoints that will be explored this way will be:

- Superficial plexus depth (µm) (day 1, day 15, day 29, day 57)
- Mean blood vessel diameter (µm) (day 1, day 15, day 29, day 57)
- Blood vessel density (day 1, day 15, day 29, day 57)
- Collagen matrix index (day 1, day 15, day 29, day 57)
- Carboxylate levels (day 1, day 15, day 29, day 57)
- Stratum corneum lipid structure (day 29)

Furthermore, summaries of the key outcomes (TEWL and epidermal thickness) by visit (day 1, day 15, day 29) will be made split by FLG loss-of-function mutation carriers.

Exposure and Compliance

A summary of the number of treatment days and the used weight per treatment day by treatment will be provided.

7.4 Adverse event data:

All Adverse Events will be summarized for all subjects enrolled in the study – both the number of participants with an AE and the total number of AEs. AEs will be tabulation by system organ class and by preferred term, as well as severity and relationship to treatment. Finally, those AEs which are specifically recorded as related to one of the test sites, the AEs will be summarised by test site. A listing, by participant number, will be produced to show the AEs at the worst severity and worst relationship to treatment.

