The data from this study will then be used to identify and refine biophysical biomarkers of skin atrophy and skin barrier disruption in steps 2 and 3. In a second clinical study the validity of the newly identified biomarkers will be demonstrated (outside the scope of this protocol).

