4.3 Exploratory objectives

The following exploratory objectives relate to research questions 1 and 2:

- To investigate whether OCT-derived biomarkers (other than the established structural OCT biomarker) enable the accurate quantification of tissue changes (vascular and matrix) associated with epidermal atrophy in response to TCS treatment. Biomarker measurements from the images will include:
 - Superficial plexus depth (μm) from angiographic OCT images¹⁰
 - Mean vessel diameter (μm) from angiographic OCT images¹⁰
 - Vessel density (segments/mm²) from angiographic OCT images¹⁰
 - Collagen matrix index (an index derived from birefringence images of collagen density and arrangement) from polarisation sensitive OCT images^{11,12}
- To investigate whether FTIR spectroscopy-derived biomarkers enable the accurate quantification of skin barrier condition and function in response to TCS treatment. Biomarker measurements from the spectra will include:
 - NMF levels in the skin^{13,14}
 - Lipid Structure^{15,16}
- To investigate the number of participants with *FLG* loss-of-function mutations and explore if there is any evidence of a relationship to treatment effects
- To identify (by completing the objectives above) a panel of biomarkers that best characterises epidermal atrophy. The biomarkers identified will be taken forward into the next stage of the research program.

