10.4.4 Exploratory outcome analysis

The primary and secondary analyses will identify where there is evidence of a difference between crisaborole ointment and betamethasone valerate cream in the change from baseline and which biomarkers are able to identify this difference in the clinical trial setting.

The exploratory analysis will investigate whether a sub set of the OCT endpoints can be used to non-invasively identify skin changes. This analysis will use multiple logistic regression to determine which of the new biomarkers provide the most informative and sensitive data pertaining to the atrophic changes induced by TCS treatment. This will be accomplished by assessing the ability of each biomarker to differentiate the skin of participants before and after treatment with the potent TCS, which is known to induce sub-clinical atrophic skin changes within the treatment window.

The biomarker (or subset of biomarkers) which are identified by this analysis will also be recorded in a subsequent study comparing crisaborole to a moderately potent TCS. This will enable the confirmation of the ability of the biomarkers to identify skin changes in a second independent dataset.

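### SAP 7.3 selects the biomarker panel from before and after values of the same forearms, with no provision for the pairing and no internal validation

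*SAP*

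**What the plan says.** SAP 7.3 states that "Discriminant analysis will be used to determine which of the new biomarkers provide the most informative and sensitive data". The criterion is "assessing the ability of each biomarker to differentiate the skin of participants before and after treatment with the potent TCS". Six markers are listed: superficial plexus depth, vessel diameter, vessel density, collagen matrix index, carboxylate and stratum corneum lipid structure. The section does not say how two values from one participant enter the analysis, which visit counts as after, what rule admits a marker to the panel, or how discrimination is measured and validated. The SAP's list of tables, figures and listings contains no discriminant-analysis output.

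Protocol 10.4.4 describes the same step differently: "This analysis will use multiple logistic regression to determine which of the new biomarkers provide the most informative and sensitive data". SAP 7.9 declares only the interim analysis as a change from the protocol.

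On what happens to the panel, protocol 4.3 says: "The biomarkers identified will be taken forward into the next stage of the research program". Protocol 10.4.4 adds: "This will enable the confirmation of the ability of the biomarkers to identify skin changes in a second independent dataset".

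**The concern.** Deriving the panel is one of the study's stated aims (SAP section 1), and the next study depends on the result. The groups to be separated are two measurements of the same skin. Ordinary discriminant analysis and ordinary logistic regression both treat each row as a separate unit. They compare the shift with the spread between people rather than with the spread of within-person change. If the fitted rule is then scored on the data that produced it, its accuracy is above chance even when no marker carries information.

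Two errors are possible. A useless marker may look mildly informative, or a real marker with a small but consistent within-person shift may be dropped. The second is harder to repair, because the markers selected here are the only ones that protocol 10.4.4 commits the next study to record.

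**Working it through.** **Inputs.** There are 33 completers (protocol 10.1 and 10.2) and tests are two-sided at 5% (SAP 7.5). Five markers can enter a before/after comparison, because lipid structure is defined at day 29 only (protocol 4.7, SAP 6.3 and 7.3). The before-after correlation ρ is not given, so it is assumed to run from 0 to 0.9. Markers are assumed independent of each other.

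**The plan's own figure.** A difference of 3.55 µm with SD 5 µm, 80% power and a two-sample t-test needs 32.13 per group, rounded up to 33. Allowing 10% dropout, 33 / 0.9 = 36.7, so 37. Both figures reproduce. The documents give no figure for the selection step, so 33 pairs is used below.

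**Optimism.** Each run draws 33 before/after pairs on five markers with no true change. The rule is w = S⁻¹(m_after − m_before), with S the pooled covariance and the cut-off at the midpoint of the two group means. Apparent accuracy scores the same 66 rows (1,000 runs). The validated figure leaves out both rows of one participant at a time (200 runs).

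| ρ | Mean apparent accuracy | 95th percentile | Mean apparent AUC | Leave-one-participant-out accuracy |
|---|---|---|---|---|
| 0 | 0.61 | 0.68 | 0.65 | 0.50 |
| 0.5 | 0.58 | 0.65 | 0.61 | 0.49 |
| 0.9 | 0.54 | 0.59 | 0.55 | 0.50 |

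The validated figures are chance level within simulation error.

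**Lost power, one marker shifted by 0.5 SD of a single visit's values.** The paired t-test has noncentrality √33 × 0.5 / √(2(1 − ρ)) on 32 degrees of freedom. The unpaired statistic is centred near 0.5 / √(2/33) = 2.03 whatever ρ is. That is close to its critical value of about 2.00, so its power stays near one half (simulated, 20,000 runs).

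| ρ | Paired noncentrality | Paired power | Unpaired power |
|---|---|---|---|
| 0 | 2.03 | 0.50 | 0.52 |
| 0.5 | 2.87 | 0.80 | 0.52 |
| 0.7 | 3.71 | 0.95 | 0.53 |
| 0.9 | 6.42 | 1.00 | 0.55 |

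For a smaller shift of 0.3 SD, simulated unpaired power falls from 0.23 at ρ = 0 to 0.03 at ρ = 0.9, while paired power rises from 0.22 to 0.96.

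**Timing of the inputs.** SAP 7.3 lists collagen matrix index on days 1, 15, 29 and 57, but PS-OCT is done on days 1 and 29 only (protocol 4.7 and Table 7.1). Day 29 is therefore the only after visit at which all five markers can be compared with day 1.

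**The case against.** The strongest reply is that the panel is meant to be provisional. Protocol 3.4 calls it preliminary, protocol 10.4.3 says "A future study is planned to confirm the selection of biomarkers from this study", and protocol section 3 says "In a second clinical study the validity of the newly identified biomarkers will be demonstrated". A reader might infer from SAP 7.3 that the panel is never validated. These passages rule that out: only internal validation is missing. The planned confirmation still has two limits. A marker dropped here has no committed second look. The next study also uses a moderately potent steroid (protocol 3.3 and 10.4.4), so a marker that fails there may have been falsely selected here or may reflect a weaker drug effect.

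A reader might also infer that the SAP treats the before and after values as independent groups. It does not say so. It is silent, and SAP 7.1 and 7.2 use a subject random effect or a paired analysis for other endpoints. The point is that the named method, in its ordinary form, ignores pairs and nothing in SAP 7.3 departs from that form.

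The two harms also pull in opposite directions. At ρ = 0 ignoring the pairs costs no power. At ρ = 0.9 the optimism is only about 0.04. An overall unpaired multivariate test on five null markers rejects at 0.053 at ρ = 0 and almost never from ρ = 0.5 upward, so false formal significance is not the danger. This stands. SAP 7.3 also speaks of each biomarker, so a joint five-marker rule is an assumption. If each marker were instead judged alone by a correctly sized 5% test, the chance of at least one false selection would be 1 − 0.95⁵ = 22.6% with independent tests.

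Finally, before versus after on one forearm mixes drug effect with time, but it would go too far to say that the plan ignores the other forearm. Protocol 4.7 already defines the OCT and carboxylate outcomes as differences in change between treatments. Crisaborole is not a neutral control for time either, since protocol 3.3 notes that its base may itself benefit the barrier.

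**Conclusion.** The concern holds. As specified, panel selection makes no provision for the pairing, has no internal check on optimism, and uses a different method from the protocol without declaring the change. With five null markers, apparent accuracy overstates the truth by about 0.04 to 0.11 on average. For a 0.5 SD shift, ignoring the pairs costs nothing at correlation 0, about 0.27 of power at 0.5 (0.80 − 0.52 = 0.28 from the rounded figures) and more above that. These sizes rest on an assumed correlation, independent markers and the ordinary form of the method.

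A reader might conclude that an uninformative panel will be presented as proven. The documents do not support that: no performance measure is prescribed, the analysis is labelled exploratory, and the optimism is moderate. Even so, apparent accuracy near 0.6 could not be told from a weak real signal without a validated figure beside it. A better analysis is available from data already being collected.

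**What to change.** Amend SAP 7.3 as follows:

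- Define after as day 29. Base selection on within-participant day 29 minus day 1 changes on the betamethasone forearm, ranked by standardised paired change. If a combined rule is wanted, use a matched-pair model such as conditional logistic regression. State the rule that admits a marker.
- Report leave-one-participant-out discrimination, with the selection step repeated inside each loop.
- Show the betamethasone-minus-crisaborole difference in change alongside as support, noting that the crisaborole base may affect the barrier.
- Assess lipid structure only by the day 29 difference between forearms, and correct the collagen index days.
- Name one method in the SAP and protocol 10.4.4, list the change in SAP 7.9, and add the output to the table list.

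The cost is SAP wording and a little more programming. Reported discrimination will be lower than the in-sample figure.
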